1. PROJECT TITLE

Human Psychophysiological Correlates of Sensorimotor Functioning

4. ESTIMATED DURATION OF THE STUDY

7 years from original date of approval

5. LAY LANGUAGE SUMMARY OR SYNOPSIS

These studies assess information processing and neurocognition in clinically normal individuals and in individuals with specific brain disorders. In some cases, studies assess the effects of medications on information processing and neurocognition, either as a means to understand the biological mechanisms that control these processes, or as a way to test the potential clinical value of medications for improving these processes in patients with brain disorders.

6. SPECIFIC AIMS

Certain neuropsychiatric disorders are characterized by a brain-based deficit in the ability to effectively inhibit, or "gate" sensory, cognitive or motor information. To study the physiological basis of this inhibitory deficit, we use prepulse inhibition of the acoustic startle reflex as an operational measure of sensorimotor gating. We study the acoustic startle reflex, including prepulse inhibition (PPI) and prepulse facilitation of startle in neuropsychiatric patients and appropriate control comparison populations.

A substantial literature of preclinical studies demonstrates that prepulse modification of the startle reflex, including PPI, is regulated by specific neurochemical substrates. Among these, brain dopamine (DA) activity is known to regulate PPI via D2-family receptors in portions of the striatum. PPI is disrupted or eliminated in rats by systemic or intracerebral treatment with DA agonists. These and related animal studies have allowed us to identify a specific neural circuitry, connecting limbic cortical structures, through their basal ganglia efferents, to pontine structures, that regulates the amount of sensorimotor gating, as measured by PPI. It would be critically important to determine whether these same substrates regulating PPI in rats, could be extrapolated to humans, and thus allow us to interpret the neural basis for abnormal patterns of PPI in neurologic and psychiatric patients.

In a series of studies, we investigated the neurochemistry of PPI in humans, by documenting changes in PPI in response to specific pharmacologic probes, using adequate sample sizes, agonist-antagonist interactions and informative dose-response profiles where possible. The similarities and differences between the responses to pharmacological manipulations in humans and rats provide important evidence for understanding the neural circuit substrates of PPI in humans.

Differences in sensorimotor gating also distinguish certain groups of normal subjects. For example, lower levels of PPI are found in clinically normal individuals who carry the Val/Val vs. Met/Met alleles for the Val158Met polymorphism of the gene for catechol-O-methyltransferase. In other cases, differences in PPI drug sensitivity distinguish certain groups of normal subjects. For example, amphetamine differentially changes PPI among individuals characterized as having low vs. high novelty seeking personalities. For these reasons, some of our studies interrogate specific genetic and personality characteristics of our test subjects: genotyping is conducted using blood samples, and specific questionnaires are used to evaluate personality and behavioral characteristics of the study populations.

Differences in sensorimotor inhibition will be detected by some, but not other laboratory-based measures, reflecting differences in the particular psychophysical demands of the measure. To add to our

understanding of patterns of sensorimotor inhibition across normal and patient populations, and of changes in sensorimotor inhibition in response to specific manipulations of brain circuitry thought to regulate one form of sensorimotor inhibition (PPI), we also assess Latent Inhibition, Negative Priming, Mismatch Negativity and Gamma Band Synchronization in some of our study groups.

Importantly, measures of sensorimotor gating are associated with higher brain functions, including neurocognitive processes. Thus, in some cases, our subjects complete measures of neurocognition, designed specifically to assess drug effects on processes such as working memory. In this way, we can test the hypothesis that drug-induced increases in sensorimotor gating can contribute to neurocognitive improvements in patients populations.

Our current studies are designed to achieve 3 Specific Aims (see Figure 1):

1. To assess the effects of the indirect dopamine agonist, d-amphetamine, on PPI and neurocognition in healthy subjects, and the moderating roles of personality and genotype in these effects. 120 healthy subjects will complete a within-subject study of placebo vs. 20 mg amphetamine (p.o.) on two separate days, completing measures of sensorimotor gating and neurocognition on each test day. All subjects will be characterized in terms of specific genetic and personality characteristics.

2. To assess the effects of the NMDA antagonist, memantine, on PPI and neurocognition in healthy subjects, and the moderating roles of personality and genotype in these effects. 30 healthy subjects will complete a within-subject study of placebo vs. 20 mg memantine (p.o.) on two separate days, completing measures of sensorimotor gating and neurocognition on each test day. All subjects will be characterized in terms of specific genetic and personality characteristics.

3. To assess the effects of the NMDA antagonist, memantine, on PPI and neurocognition in schizophrenia patients, and the moderating roles of genotype in these effects. 60 well-characterized and clinically stable individuals with schizophrenia will complete a within-subject study of placebo vs. 10 mg memantine (p.o.) (n=30) or placebo vs. 20 mg memantine (n=30) on two separate days, completing measures of sensorimotor gating and neurocognition on each test day. All subjects will be characterized in terms of specific genetic characteristics.

BACKGROUND AND SIGNIFICANCE 7.

The startle reflex is a constellation of responses to sudden, relatively intense stimuli that is usually classified as a defensive response. One major advantage of startle response paradigms is that the same phenomena can be studied across species. In humans, the blink reflex component of the startle response is measured using electromyography of the orbicularis oculi muscle. Despite its simplicity, startle demonstrates several forms of plasticity - including habituation and fear-potentiation - that are regulated by forebrain circuitry. Even these more complex processes exhibit striking similarities across species, from rodents to humans. One form of startle plasticity is "prepulse inhibition" (PPI), which is the normal suppression of the startle reflex, which occurs when the intense startling stimulus is preceded by a weak prestimulus.

In PPI, a weak prepulse inhibits a reflex response to a powerful sensory stimulus. PPI occurs when the prepulse and startling stimuli are in the same or different sensory modalities. PPI also occurs in virtually all mammals and primates, including humans. It is not a form of conditioning, since it occurs on the first exposure to the prepulse and pulse stimuli, and it does not exhibit habituation or extinction over multiple trials. PPI thus appears to reflect the activation of a ubiguitous "hard-wired" centrally mediated behavioral "gating" process. The PPI paradigm has been widely applied in studies of information processing in normal animals and humans. The inhibitory processes activated by the weak "prepulse" and the resulting decrement in startle amplitude are used in an operational definition of sensorimotor gating: the degree to which startle amplitude is inhibited by a prepulse is a measure of the amount of sensorimotor gating.

Our interest in PPI as a measure of sensorimotor gating grew from the observation that human disorders characterized by dysfunction in brain substrates that regulate PPI are accompanied by evidence of impaired cognitive or sensorimotor inhibition. Thus, our laboratory and others have reported impaired PPI in patients with Schizophrenia, Obsessive Compulsive Disorder (OCD), Huntington's Disease, nocturnal enuresis and Attention Deficit Hyperactivity Disorder or Tourette's Syndrome. These disorders are all characterized by a loss of gating in sensory, motor or cognitive domains, and are characterized neurologically by abnormalities in cortico-striato-pallido-pontine circuitry that modulates PPI.

Over the past 20+ years, the PI and colleagues have systematically studied the neural substrates of PPI in rats. These studies have revealed that PPI is regulated by sequential neural connections between limbic cortex (temporal and medial prefrontal cortex), the ventral striatum, the ventral pallidum and the pontine tegmentum. This limbic cortico-striato-pallido-pontine circuitry then interfaces with the primary startle circuit at the level of the nucleus reticularis pontis caudalis. The neurotransmitters active at each level of this circuitry have been studied as well: the cortico-striatal interface involves interactions between glutamate and D2 dopamine receptors; the striato-pallidal input is GABAergic, as is the pallido-pontine input. Thus, by identifying patterns of PPI deficits in neuropsychiatric populations, we are able to use this information to understand the pathophysiology of these disorders, as well as to develop strategies for designing optimal drug treatments. We have already made significant steps towards these ends.

Some evidence already suggests that findings from preclinical studies of the neural substrates regulating PPI can "cross species" and be applied to humans. For example, PPI is disrupted in patients with Huntington's Disease (HD), and in rats with cytotoxic lesions of striatal regions that model features of the pathophysiology of HD. Preliminary studies suggest that the "cross-species" parallels of this measure can also be demonstrated with pharmacologic probes: PPI is disrupted in both rats and humans by indirect DA agonists (e.g. amphetamine) and by direct DA agonists (e.g. bromocriptine and apomorphine). These pharmacologic studies of PPI in humans are not fully compelling at this time, since they were either performed only in small samples, or in patients with neurologic disorders (e.g.. Parkinson's Disease) that might complicate interpretation of the findings as they relate to the normal neural regulation of PPI.

More recent studies have clarified that the sensitivity of PPI to drug effects in normal humans is moderated by several factors, including the presence of specific genes, and personality dimensions associated with those genes. For example, several groups have reported that PPI and its sensitivity to drug challenge differs significantly between normal men who carry different alleles for the COMT Val158Met polymorphism. In these studies, the Val/Val allele is associated with high COMT activity, rapid DA catabolism, high novelty seeking scores, low basal PPI and PPI-enhancing effects of the COMT inhibitor, tolcapone. In contrast, the Met/Met allele is associated with low COMT activity, low DA catabolism, low novelty seeking scores, high basal PPI, and PPI-reducing effects of tolcapone. We previously reported that rats expressing high levels of COMT within the ventral striatum exhibit PPIenhancing effects in response to DA agonists, like amphetamine, while rats expressing low levels of COMT in this region exhibit PPI-reducing effects in response to amphetamine. More recently, we confirmed that normal women with high novelty seeking scores (who as a group predominantly express the Val/Val high activity COMT allele) respond to amphetamine with elevations of PPI, while those with low novelty seeking (associated with the Met/Met low activity COMT allele) respond to amphetamine with reduced PPI. We also detected PPI-enhancing effects of the NMDA antagonist and weak DA agonist, memantine, among men exhibiting low baseline PPI and/or high novelty seeking, both of which are associated with the Val/Val COMT genotype. Thus, across species, genetically determined levels of COMT activity appear to moderate the impact of specific drugs on sensorimotor gating. These findings suggest a biological explanation for a genetically based "vulnerability" to the gating-disrupted effects of increased dopamine activity and/or reduced NMDA activity, thought to be core features of brain disorders such as schizophrenia and Tourette Syndrome. We now plan to extend this work to further clarify the role of COMT polymorphisms and other genetic substrates on the sensitivity of PPI to drug effects in humans.

The most recent development in our studies has emerged as other groups, as well as our own, have reported that levels of PPI are significantly associated (correlated) with specific neurocognitive processes, including measures of executive functioning and working memory. In the process of our pharmacological

studies of PPI, we identified specific agents (e.g. memantine) that increased PPI, particularly among individuals with specific physiological (e.g. low baseline PPI) and psychological (e.g. high novelty seeking) "biomarkers" associated with the Val/Val COMT polymorphism. These two lines of findings led us to test whether such drug-induced increases in PPI predicted increases in neurocognitive functions in biomarker-identified subgroups. If so, we might be able to develop laboratory-based measures for predicting procognitive drug effects in patient populations - particularly among disorders associated with impaired PPI and working memory, such as schizophrenia.

In total, we expect to accomplish three goals by extending a new line of research, investigating the effects of specific pharmacologic agents on PPI and other psychophysiological measures in humans:

1) Extension of the preclinical findings into humans, to allow interpretation of anatomical and genetic correlates of observed behavioral deficits in psychiatric patients.

2) Replicate and extend findings in humans with specific pharmacologic probes.

3) Determine the relationship between specific drug effects on PPI and neurocognitive functions, in healthy and patient populations, as a function of specific physiological, psychological and genetic biomarkers.

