As described in our past progress reports, we continue to actively test subjects using our proposed measures. They include bilateral measures of eyeblink acoustic startle, prepulse inhibition and habituation of acoustic startle, visuospatial priming and latent inhibition. Additional variations of these measures are developed on a regular basis to enhance their sensitivity.

After completing a series of studies using the non-DA stimulant caffeine, we undertook a systematic series of studies to examine the effects of DA agonists on startle and related measures in normal humans. We assessed the time course of action of several DA agonists - pergolide (0.025 and 0.1 mg), amphetamine (20 mg), amantadine (200 mg) and bromocriptine (1.25 and 2.5 mg) - on startle measures,

autonomic changes, and self-ratings of somatic and physiological symptoms. We then completed detailed, within-subject studies of the effects of amphetamine, amantadine, bromocriptine and pramipexole on PPI and related measures. Findings from these studies were described in published reports, cited in Section 22, and many have already been replicated and extended by other groups.

Most recently, we have begun to assess the broader neurocognitive correlates of drug-induced changes in sensorimotor gating. Our group and others have reported that levels of PPI correlate significantly with global neurocognitive measures, and specifically, with working memory (WM); in schizophrenia patients, we reported that levels of PPI correlate significantly with global levels of functioning. We also reported that the Alzhemier's Disease medication and NMDA antagonist, memantine, significantly increases PPI,

particularly among individuals with phenotypes - low baseline PPI and high novelty seeking - associated with the Val/Val COMT genotype. As a result, we have initiated studies in normal subjects to test the hypothesis that memantine will increase WM, particularly among subjects exhibiting high memantine PPI sensitivity. Our initial findings in a double-blind, within-subject, balanced

Effects of memantine (MEM) vs. placebo (PBO) on WM (%ile score from MCCB, see text). WM was increased by MEM in 7 out of 8 subjects, and unchanged in the 8th. In these subjects (F=10.68, p<0.015), MEM also significantly increased PPI. This ongoing study is conducted with a double- blind, balanced order design.	WM	РВО	* MEM
--	----	-----	----------

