For example, to assess the effects of memantine on "gating" measures in schizophrenia patients, the primary measure will be evaluated by 2-way repeated-measure ANOVA of PPI with memantine dose and prepulse interval as within-subject factors. The hypothesis that memantine will increase PPI in schizophrenia patients will be confirmed by a significant effect of dose (active > PBO) or significant dose x interval (int) interaction and post-hoc comparisons at one or more prepulse intervals. Existing data (see above) provide a strong *a priori* prediction that the 120 ms prepulse interval will be most sensitive to PPI-enhancing effects of MEM. The effect size (d) for PPI-enhancement by 20 mg memantine in HCS was 0.91; with a similar "d" in patients, 30 patients/dose yields power of 0.92 to detect the predicted memantine effects; with maximum expected attrition (n=24), power is 0.85. Past findings also lead to the prediction that these MEM effects would be most robust in subjects exhibiting the lowest basal PPI levels (d=1.80). Using a median split of mean basal (screening) PPI levels, ANOVA as above will detect a significant interaction of memantine dose x basal PPI level, or dose x basal level x int, and significant post-hoc comparisons at one or more prepulse intervals (again, 120 ms being the strongest *a priori* candidate). Given the published "d" in control subjects, a comparable "d" in the proposed 12-15 "low PPI" patients/dose group would yield power >0.95 to detect the predicted memantine effects.

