Main effects of memantine on WM will be tested by one-way ANOVA with memantine dose as a withinfactor. Based on d=0.73 for increased WM after 20 mg MEM in controls (see above), the proposed 30 patients/dose group would yield power of 0.79 to detect significant WM-enhancing effects. While preliminary data yield less robust predictions for COMT subgroup sensitivities in memantine effects on WM performance, given the significant correlation of WM and PPI, and known impact of COMT genotype on PPI levels, we predict some differential (Val/Val > Met/Met) memantine sensitivity in this measure. If we estimate effects of COMT status on WM memantine-sensitivity to be comparable to those for PPI (65% increase in effect size), then the estimated d for Val/Val vs. Met/Met sensitivity should be 1.20, and the proposed genotype subgroup sizes would yield power of 0.65 to detect genotype-sensitive memantine effects on WM.

Secondary "biomarkers" are MMN and GBS. For MMN, positive memantine effects will be detected by increased MMN amplitude at electrode Fz. For GBS, positive memantine effects would be detected by increased 40 Hz evoked power at electrode Fz. Unlike those for PPI, predictions of positive memantine effects on MMN and GBS are not based directly on previous findings from our laboratory, using measures identical to those proposed herein. However, based on reports in healthy subjects from other laboratories of memantine effects on MMN (d=0.87) and ketamine effects on GBS (d=0.69), the proposed 30 patients/dose group would yield power of 0.90 and 0.75, respectively, to detect positive memantine effects on these measures.

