Statistical Analysis Plan Memantine Effects on Sensorimotor Gating and Neurocognition in Schizophrenia NCT03860597 R01MH094320 Latest IRB approval date: June 21, 2022 IRB expiration date: July 7, 2023

The primary statistical considerations for these data are those required to test the primary hypothesis that memantine (MEM) would enhance sensorimotor gating and related measures of auditory information processing in schizophrenia (SZ) patients. The operational measure of sensorimotor gating was prepulse inhibition of startle (PPI). The primary hypothesis was tested by a 2-way repeated-measure ANOVA of PPI with MEM dose and prepulse interval (10, 20, 30, 60 or 120 ms) as within subject factors. The key dependent measure was %PPI, calculated according to common practices in the literature. The hypothesis that MEM will increase PPI in SZ patients was to be confirmed by a significant main effect of drug (active > PBO) or significant interaction among the variables of drug, dose (10 or 20 mg), diagnosis (healthy subject (HS) or SZ) or prepulse interval, and informative post-hoc comparisons. The assumptions behind these analyses range from the standard assumptions underlying the use of parametric analyses, to those specific to prepulse inhibition, e.g. related to the potential confounding effects of drug or diagnosis effects on startle magnitude. Data were demonstrated to be normally distributed and drug effects on PPI were shown to be independent of changes in startle magnitude. Analyses confirmed the hypothesis for the 20 mg dose of MEM in SZ patients.

The operational measure of mismatch negativity (MMN) is mean amplitude in response to oddball stimuli over the 135-205 ms range. The primary hypothesis was tested by an ANOVA of MMN with MEM dose as a within subject factor. The hypothesis that MEM will increase MMN in SZ patients was to be confirmed by a significant main effect of drug (active > PBO) or significant interaction among the variables of drug, dose (10 or 20 mg), diagnosis (healthy subject (HS) or SZ), and informative post-hoc comparisons. The assumptions behind these analyses range from the standard assumptions underlying the use of parametric analyses. Data were demonstrated to be normally distributed. Analyses confirmed the hypothesis for the 20 mg dose of MEM in SZ patients.

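### The stated hypothesis that drug-induced PPI gains go with neurocognitive gains has no direct analysis in the protocol or the SAP

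*Protocol*

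**What the plan says.** The link between the two responses is stated in several places in the protocol.

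- Section 6 (Specific Aims), before the numbered aims: "we can test the hypothesis that drug-induced increases in sensorimotor gating can contribute to neurocognitive improvements in patients populations".
- Section 7 (Background and Significance): two lines of findings led the investigators to "test whether such drug-induced increases in PPI predicted increases in neurocognitive functions in biomarker-identified subgroups". Goal 3 in the same section reads "Determine the relationship between specific drug effects on PPI and neurocognitive functions, in healthy and patient populations", and it ends by making that relationship a function of physiological, psychological and genetic biomarkers.
- Section 8 (Preliminary Studies), on healthy subjects: studies were begun to "test the hypothesis that memantine will increase WM, particularly among subjects exhibiting high memantine PPI sensitivity".

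The analyses are in section 9.j. For PPI in patients, "the primary measure will be evaluated by 2-way repeated-measure ANOVA of PPI with memantine dose and prepulse interval as within-subject factors", with a median split on basal PPI and COMT genotype as moderators. For cognition, "Main effects of memantine on WM will be tested by one-way ANOVA with memantine dose as a withinfactor", with a predicted COMT difference. Mismatch negativity (MMN) and gamma band synchronization (GBS) are tested for drug effects. The only mention of a WM-PPI relation is a reason for that COMT prediction: "given the significant correlation of WM and PPI, and known impact of COMT genotype on PPI levels".

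The SAP is titled "Memantine Effects on Sensorimotor Gating and Neurocognition in Schizophrenia". Its analyses cover PPI, MMN and the auditory steady-state response (ASSR), and no cognitive outcome.

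**The concern.** The hypothesis concerns two changes in the same person: those whose PPI rises on drug should tend to be those whose cognition rises. A drug effect on mean PPI and a drug effect on mean WM are two group averages. Both can be positive when the people who gain on one measure are not the people who gain on the other.

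What is at stake is the use to which the result would be put. Section 8 reports parallel rises in WM and PPI in 8 healthy subjects, gives no association between the two changes, and goes on to suggest that such a pattern in patients could identify in advance those who will benefit. Followed exactly, the plan would give no better evidence in patients. It would produce no estimate, and no confidence interval, for goal 3.

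**Working it through.** **1. The plan's own figures.** Section 9.j states power for the separate drug effects. A noncentral t calculation with two independent groups of size n and two-sided alpha 0.05 (the protocol gives alpha but not sidedness) comes within 2 points of each:

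| Outcome | d | n | Stated | Recomputed |
|---|---|---|---|---|
| PPI | 0.91 | 30 | 0.92 | 0.934 |
| PPI, after attrition | 0.91 | 24 | 0.85 | 0.870 |
| WM | 0.73 | 30 | 0.79 | 0.794 |
| MMN | 0.87 | 30 | 0.90 | 0.912 |
| GBS | 0.69 | 30 | 0.75 | 0.748 |

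A paired t calculation does not reproduce them (0.972 for WM, 0.998 for PPI at n=30). None of these figures concerns the link between outcomes.

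**2. Does any planned model contain both quantities?**

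| Analysis | Outcome | Explanatory terms | Links PPI change to cognition? |
|---|---|---|---|
| 9.j, gating | PPI | dose, interval | no |
| 9.j, basal split | PPI | dose, interval, screening PPI | no; basal level is not change |
| 9.j, COMT | PPI | genotype, dose, interval | no |
| 9.j, WM | WM | dose; COMT prediction | no |
| 9.j, biomarkers | MMN, GBS | dose | no |
| SAP | PPI, MMN, ASSR | drug, dose, diagnosis (interval for PPI) | no |

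The possible logistic regressions in 9.j use genotype as the predictor. The general sentence on other dependent measures offers ANOVAs of single outcomes.

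**3. Can separate effects stand in for the link?** Simulation: 20,000 trials, n=30, mean standardised changes 0.91 (PPI) and 0.73 (WM), a paired t-test on each, and a test of the correlation of the changes.

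| True correlation of changes | Both drug effects significant | Correlation test significant |
|---|---|---|
| -0.3 | 97.1% | 36.7% |
| 0 | 96.9% | 4.9% |
| 0.3 | 97.1% | 37.1% |
| 0.5 | 97.0% | 83.0% |

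The 97% level assumes that d is the standardised within-subject change, which the protocol does not say. The power of each separate test does not depend on the correlation under either reading of d.

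**4. What a direct analysis could detect.** The documents give no expected correlation, so r is shown as a range. By Fisher z, the r detectable with 80% power is tanh((1.960 + 0.842)/√(n−3)).

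- n=24 (one dose, maximum expected attrition): tanh(2.802/4.583) = 0.545
- n=30 (one dose, or the healthy memantine sample): tanh(2.802/5.196) = 0.492
- n=48 (pooled, 2 × 24): tanh(2.802/6.708) = 0.395
- n=60 (pooled, 2 × 30): tanh(2.802/7.550) = 0.355

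Power at r = 0.2, 0.3, 0.4, 0.5 is 0.18, 0.36, 0.60, 0.81 at n=30, and 0.33, 0.65, 0.89, 0.99 at n=60. For an observed r of 0.30, the 95% CI is tanh(0.3095 ± 1.96/√(n−3)): −0.07 to 0.60 at n=30, and 0.05 to 0.51 at n=60. Each covariate takes one more from n−3. With test order, n=30 gives tanh(2.802/√26) = 0.50. With order and dose group, n=60 gives tanh(2.802/√55) = 0.36.

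**5. Why test order matters.** With two test days, a practice or day effect enters both change scores with a sign set by the order. If order shifts each change by ±k within-order SDs in the same direction, and there is no other association, the induced correlation is k²/(1+k²). For k=0.5 that is 0.25/1.25 = 0.20; for k=0.3 it is 0.09/1.09 = 0.08. The k values are assumptions.

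**The case against.** The strongest reply is that this link is not what the trial set out to test. A reader might infer that the trial's central hypothesis has been left unanalysed. The documents do not support that. All three Specific Aims are worded as drug effects plus moderation, the SAP's primary hypothesis is a drug effect on gating and auditory processing, and section 9.j does plan drug effects on PPI and WM in patients. The section 6 sentence stands ahead of the aims as motivation. It is nevertheless a stated hypothesis, and goal 3 lists it as something the work is expected to accomplish.

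A second reply is that goal 3 is framed by biomarkers, and that the predicted Val/Val over Met/Met sensitivity for both PPI and WM partly addresses it. This stands in part, so it would be too strong to say that nothing in the plan bears on the question. But parallel genotype effects are again group contrasts, and section 9.j puts the power of the WM contrast at only 0.65. The basal-PPI split does not help, because it is specified for PPI only. Nor should the WM-PPI correlation in 9.j be taken as a planned test or as the source of the WM effect size. It supports a predicted direction for COMT; the size comes from the assumed 65% increase taken from the COMT estimate for PPI.

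Third, the SAP describes only primary considerations, so its silence on cognition is weak evidence about secondary aims. That is fair. The gap rests mainly on section 9.j.

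Finally, the SAP already reports that its hypotheses were confirmed for 20 mg, so a reader should not suppose that an analysis added now would be prespecified.

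**Conclusion.** The point holds as a gap in a stated secondary question. Sections 6 and 7 promise an answer on whether PPI gains and neurocognitive gains go together, and no planned model relates the two changes within persons. The primary PPI test is unaffected.

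Separate drug effects or COMT effects are at most indirect evidence, because the same pair of significant results is about equally likely under no link, a positive link or an inverse one. A direct analysis would be of modest precision under the protocol's rule that dose groups are analysed separately, and somewhat better pooled, which section 9.j allows only for exploratory work when the doses behave alike. These sizes assume two-sided alpha 0.05, roughly bivariate normal changes and complete pairs of scores.

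Even a clear slope would show association. Two changes measured over the same pair of days cannot establish that one contributes to the other.

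**What to change.** Add to section 9.j, after the WM analysis, and to the SAP, one secondary or exploratory analysis, labelled post hoc if it is added after the results were seen:

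- Regress each patient's WM change (active minus placebo day) on the same patient's PPI change at 120 ms, the interval section 9.j already singles out, with test order as a covariate.
- Fit it in each dose group, as section 9.j requires, and add a pooled exploratory model with dose group as a further covariate.
- Apply the same model, with test order, to the healthy memantine sample, because goal 3 covers both populations.
- Report every slope with its 95% CI whatever the drug main effects show, together with the number of complete pairs. Startle non-responders are excluded from PPI analysis, and the model schedule in 9.g lists the cognitive battery as one of three alternatives, so pairs may be fewer than enrolled.
- Word the conclusion as association.

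The cost is a few regressions on measures that Aims 2 and 3 already place on both test days, plus wording. The intervals will be wide, and the claim softens from contribution to association.
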